### **6.3.1.1. Incidence of Adverse Events**

An overall summary of unsolicited TEAEs including the number and percentage of subjects who experience the following will be presented:

- Any unsolicited TEAEs
- Any serious TEAEs
- Any fatal TEAEs
- Any unsolicited medically-attended TEAEs
- Any unsolicited TEAEs leading to discontinuation from study vaccine
- Any unsolicited TEAEs leading to discontinuation from participation in the study
- Any unsolicited Grade 3/Severe TEAEs
- Any unsolicited Grade 3 or higher TEAEs
- Any unsolicited Non-serious TEAEs
- Any unsolicited Non-serious and Grade 3/Severe TEAEs
- Any unsolicited Non-serious and Grade 3 or higher TEAEs
- Any AESI of MIS-C
- Any AESI of myocarditis and/or pericarditis
- Any AESI other than MIS-C and myocarditis and/or pericarditis

The table will also include number and percentage of subjects with unsolicited TEAEs that are treatment-related in each of the above categories. Safety summary tables for booster/third dose analysis will be provided separately.

In addition, listings containing individual subject adverse event data for unsolicited AEs, unsolicited TEAEs leading to discontinuation from study vaccine, unsolicited TEAEs leading to discontinuation from participation in the study, serious AEs, unsolicited medically-attended AEs, AESI other than MIS-C and myocarditis and/or pericarditis, AESI of MIS-C and AESI of myocarditis and/or pericarditis will be provided separately for placebo-mRNA-1273 group in Part 2 open-label phase and the group receiving booster/third dose in booster/third dose analysis. In Part 2, the safety data for the original

mRNA-1273 group in open-label will be included in blinded listings with a flag for open-label phase.

### **6.3.1.2.TEAEs by System Organ Class and Preferred Term**

The following summary tables of TEAEs will be provided by SOC and PT using frequency counts and percentages (i.e., number and percentage of subjects with an event):

- All unsolicited TEAEs
- All unsolicited TEAEs that are treatment-related
- All serious TEAEs
- All serious TEAEs that are treatment-related
- All unsolicited TEAEs leading to discontinuation from study vaccine
- All unsolicited TEAEs leading to discontinuation from participation in the study
- All unsolicited Severe TEAEs
- All unsolicited Severe TEAEs that are treatment-related
- All unsolicited medically-attended TEAEs
- All unsolicited medically-attended TEAEs that are treatment-related
- All AESI of MIS-C
- All AESI other than MIS-C
- All AESI other than MIS-C and myocarditis and/or pericarditis

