### **6.3.1.1. Incidence of Adverse Events**

An overall summary of unsolicited TEAEs including the number and percentage of subjects who experience the following will be presented:

- Any unsolicited TEAEs
- Any serious TEAEs
- Any fatal TEAEs
- Any unsolicited medically-attended TEAEs
- Any unsolicited TEAEs leading to discontinuation from study vaccine
- Any unsolicited TEAEs leading to discontinuation from participation in the study
- Any unsolicited Grade 3/Severe TEAEs
- Any unsolicited Grade 3 or higher TEAEs
- Any unsolicited Non-serious TEAEs
- Any unsolicited Non-serious and Grade 3/Severe TEAEs
- Any unsolicited Non-serious and Grade 3 or higher TEAEs
- Any AESI of MIS-C
- Any AESI of myocarditis and/or pericarditis
- Any AESI other than MIS-C and myocarditis and/or pericarditis

The table will also include number and percentage of subjects with unsolicited TEAEs that are treatment-related in each of the above categories.

In addition, separate listings containing individual subject adverse event data for unsolicited AEs, unsolicited TEAEs leading to discontinuation from study vaccine, unsolicited TEAEs leading to discontinuation from participation in the study, serious AEs, unsolicited medically-attended AEs, AESI other than MIS-C and myocarditis and/or pericarditis, AESI of MIS-C and AESI of myocarditis and/or pericarditis will be provided separately.

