### **6.3.1.2. TEAEs by System Organ Class and Preferred Term**

The following summary tables of TEAEs will be provided by SOC and PT using frequency counts and percentages (i.e., number and percentage of subjects with an event):

- All unsolicited TEAEs
- All unsolicited TEAEs that are treatment-related
- All serious TEAEs
- All serious TEAEs that are treatment-related
- All unsolicited TEAEs leading to discontinuation from study vaccine
- All unsolicited TEAEs leading to discontinuation from participation in the study
- All unsolicited Severe TEAEs
- All unsolicited Severe TEAEs that are treatment-related
- All unsolicited medically-attended TEAEs
- All unsolicited medically-attended TEAEs that are treatment-related
- All AESI of MIS-C
- All AESI of myocarditis and/or pericarditis
- All AESI other than MIS-C and myocarditis and/or pericarditis

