## **6.10. Data Safety Monitoring Board**

Safety oversight will be under the direction of a DSMB composed of external independent consultants with relevant expertise. Members of the DSMB will be independent from study conduct and free of conflict of interest. The DSMB will meet at pre-specified timepoints during the study to assess safety throughout study conduct. For the 6 years to < 12 years age group, the DSMB will review cumulative safety data for approximately 300 participants enrolled at the selected dose level in Part 1 before enrollment begins in Part 2. For both the middle age group (2 years to < 6 years) and the youngest age group (6 months to < 2 years) the DSMB will review cumulative safety data in both younger age groups (2 years to < 6 years; 6 months to < 2 years) combined and at all dose levels administered in Part 1 before start of Part 2 (blinded phase) for each age group. The DSMB will operate under the rules of an approved charter that will be written and reviewed at the organizational meeting of the DSMB. Details regarding the DSMB composition, responsibilities, procedures, and frequency of data review will be defined in its charter.

If any of the study pause rules, described in protocol section 6.4, are met, the Sponsor will immediately suspend further enrollment and/or study dosing and the DSMB will convene on an ad hoc basis. The DSMB will review all available unblinded study data (as applicable) to help adjudicate any potential study pauses and make recommendations on further study conduct, including requesting additional information, recommending stopping the study, recommending changes to study conduct and/or the protocol, or recommending additional operational considerations due to safety issues that arise during the study.

The Cardiac Event Adjudication Committee (CEAC) consisting of pediatric and adult cardiologists will review suspected cases of myocarditis, pericarditis, or myopericarditis to determine if they meet CDC criteria of “probable” or “confirmed” event, and to assess severity and enable the DSMB to make recommendations to the Sponsor to continue vaccine dosing. The CEAC will operate under the rules of an approved charter that will be written and reviewed at the organizational meeting of the CEAC. Details regarding the CEAC composition, responsibilities, procedures, and frequency of data review will be defined in its charter.

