## List of Abbreviations

| Abbreviation | Definition                                    |
|--------------|---|
| AB           | antibody                                      |
| AE           | adverse event                                 |
| AR           | adverse reaction                              |
| AESI         | AEs of special interest                       |
| BMI          | body mass index                               |
| bAb          | binding antibody                              |
| BD           | booster dose                                  |
| BLA          | Biologics License Application                 |
| CI           | confidence interval                           |
| CDC          | US Centers for Disease Control and Prevention |
| CEAC         | Cardiac Event Adjudication Committee          |
| CMI          | Cell-Mediated Immunity                        |
| CRO          | contract research organization                |
| CSP          | clinical study protocol                       |
| CSR          | clinical study report                         |
| DHHS         | Department of Health and Human Services       |
| DSMB         | Data Safety Monitoring Board                  |
| eCRF         | electronic case report form                   |
| eDiary       | electronic diary                              |
| EUA          | Emergency Use Authorization                   |
| ELISA        | enzyme-linked immunosorbent assay             |
| FAS          | full analysis set                             |
| GLSM         | geometric least squares mean                  |
| GM           | geometric mean                                |
| GMFR         | geometric mean fold rise                      |
| GMT          | geometric mean titer                          |
| GMR          | geometric mean ratio                          |
| HAART        | highly active anti-retroviral therapy         |
| IgG          | immunoglobulin G                              |
| IP           | investigational product                       |
| IRT          | interactive response technology               |
| IST          | internal safety team                          |
| LAR          | legally authorized representative             |
| LLOQ         | lower limit of quantification                 |
| MAAEs        | medically-attended adverse events             |
| MedDRA       | Medical Dictionary for Regulatory Activities  |

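### The booster SAP's by-term AESI list has no myocarditis/pericarditis table, and neither SAP says whether cardiac AESI counts are site-reported or adjudicated

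*SAP*

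**What the plan says.** The SAP file contains two plans, called here the blinded-phase SAP (Part 1 open-label and Part 2 blinded phases) and the booster SAP (Part 2 open-label phase, booster doses and Part 3).

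**AESI tables.** Section 6.3.1.1 of both plans has the summary row "Any AESI of myocarditis and/or pericarditis", with separate rows for MIS-C and for AESIs that are neither. Each row also gets a treatment-related count, and each category gets its own listing. Section 6.3.1.2 of the blinded-phase SAP carries the same split into the tables by system organ class and preferred term, including "All AESI of myocarditis and/or pericarditis". Section 6.3.1.2 of the booster SAP keeps the MIS-C row and "All AESI other than MIS-C and myocarditis and/or pericarditis". Where the cardiac row would stand, it has a row for all AESIs apart from MIS-C.

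**Adjudication.** Section 6.10 of the blinded-phase SAP says that the cardiac committee (CEAC) "will review suspected cases of myocarditis, pericarditis, or myopericarditis to determine if they meet CDC criteria of" a probable or confirmed event. It is also to "assess severity and enable the DSMB to make recommendations to the Sponsor to continue vaccine dosing". Further: "Details regarding the CEAC composition, responsibilities, procedures, and frequency of data review will be defined in its charter". In the booster SAP the "Cardiac Event Adjudication Committee" appears only in the List of Abbreviations.

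**The concern.** Myocarditis and/or pericarditis is one of two AESIs named in the primary safety endpoints (blinded-phase SAP, Section 3.1). AESIs are also a primary safety endpoint after every booster or third dose (booster SAP, Section 3.3.1). A reader expects the same cardiac category to be tabulated in the same way in each phase, and the origin of each count to be known.

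The booster SAP falls short on the first expectation and both plans on the second. This matters most for mRNA-1273.214. There the primary safety endpoints are only MAAEs, SAEs, AESIs and AEs leading to discontinuation, and Section 6.3.2 provides no eDiary. AESI reporting therefore carries more of the safety conclusion in the phase whose by-term list lacks the cardiac table.

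Few cardiac cases would be expected. If the plan does not say beforehand whether a count means reported or adjudicated events, that choice can be made once the cases are known. A suspected case that the committee did not accept could also stand in a table with nothing to mark it.

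**Working it through.** No figure in the SAP depends on this point, so the check is a comparison of text.

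**Step 1: AESI rows side by side.** Write M for MIS-C, C for myocarditis and/or pericarditis, and O for any AESI that is neither.

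| Place | Row 1 | Row 2 | Row 3 |
|---|---|---|---|
| Blinded-phase SAP, 6.3.1.1 | M | C | O |
| Blinded-phase SAP, 6.3.1.2 | M | C | O |
| Booster SAP, 6.3.1.1 | M | C | O |
| Booster SAP, 6.3.1.2 | M | C or O | O |

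Three of the four lists separate the three categories. The fourth differs in one row only, and its row 2 wholly contains its row 3.

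**Step 2: what survives in the booster SAP.** Row 2 of Section 6.3.1.2 is laid out by preferred term, so cardiac preferred terms keep their own lines inside it. Section 6.3.1.1 keeps the cardiac count and percentage, a treatment-related count, and listings for the crossover group and the booster/third-dose group.

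**Step 3: can the missing table be recovered by subtraction?** Not in general at subject level. Each subject is counted once per row, so row 2 minus row 3 gives the subjects with C and without O. A child with both a cardiac and another AESI is in both rows and cancels out. The summary row gives the total with C. The by-term breakdown has to be picked out of row 2.

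**Step 4: every mention of the committee.**
- Blinded-phase SAP: the summary of changes (V2.0), the abbreviation list and Section 6.10.
- Booster SAP: the abbreviation list.

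Sections 6.3 to 6.3.1.3 of both plans, which define the adverse event outputs, contain no reference to the committee, to adjudication, or to probable or confirmed status. They also do not say whether an AESI of myocarditis and/or pericarditis is the site's report or the committee's finding. The only use stated for the classification is to support DSMB recommendations.

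**The case against.** The strongest defence has four parts.

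- **The endpoint is the AESI.** Sections 3.1 and 3.3.1 do not define it as a committee-confirmed event, and Section 6.10 gives the committee an oversight role. Reporting AESIs as such matches the endpoint. This stands, and it is why adjudicated cases need not become the sole or primary cardiac row. That would be a debatable preference.
- **The source may be settled elsewhere.** The protocol, the committee charter and the table shells are not at hand, and a shell could already carry an adjudication column. This stands as a limit on what can be claimed. It does not remove the gap: both introductions give the SAP the job of supplying analysis details and derivations, and the matters that Section 6.10 leaves to the charter do not include how results are tabulated.
- **The row in the booster SAP is probably a drafting slip.** Agreed. It still leaves that plan at odds with its own Section 6.3.1.1.
- **Nothing is lost.** Largely right, as Step 2 shows.

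A reader might infer that cardiac events will be reported unadjudicated, with rejected cases kept in and confirmed cases recorded under another term left out. The SAP does not say so; it leaves the source open.

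A reader might also put a number on the stakes. With 3,000 vaccinated children (the planned maximum per age group in Part 2), the two-sided 95% Clopper-Pearson upper limit is 0.123% for 0 cases, 0.186% for 1 and 0.241% for 2. The first step is a rise of about half (0.186/0.123 = 1.51) and the second about 30% (0.241/0.186 = 1.30). The arithmetic is right, but neither plan specifies an interval or an excluded risk for AESIs. The 3,000 is also a blinded-phase maximum, while Part 3, covered by the booster SAP, enrolled 91.

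**Conclusion.** The point holds as two limited reporting defects.

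1. Section 6.3.1.2 of the booster SAP contradicts Section 6.3.1.1 of the same plan and Section 6.3.1.2 of the blinded-phase SAP. One of three AESI rows is wrong, two rows overlap, and a named primary-safety AESI has no by-term table of its own. This can be seen from the text alone.
2. No table or listing specified in either plan uses the committee's classification, and neither plan states the source of the cardiac AESI counts. This rests on the SAP text only; the protocol, charter or shells may supply the answer.

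No power, sample-size or error-rate figure changes. The first defect is a minor correction. The second is worth fixing because the classification is already to be produced and its place in the reporting should be fixed before results are known.

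**What to change.** (a) In Section 6.3.1.2 of the booster SAP, replace the row for all AESIs other than MIS-C with "All AESI of myocarditis and/or pericarditis", so that it agrees with Section 6.3.1.1 of the same plan and with the blinded-phase SAP.

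(b) In Section 6.3.1.1 of both plans, state whether the cardiac AESI row rests on the site's report or on the committee's classification. Add one summary or listing that shows the committee's probable or confirmed status beside the reported AESI, by dose and days since the last dose.

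Cost: a wording change for (a); a sentence and one added output in each plan for (b). The downside is that committee results must be loaded and reconciled before database lock, and nothing in the SAP shows that they are already in the clinical database. No dosing or clinical rule is affected.

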### **6.3.1.3.TEAEs by System Organ Class, Preferred Term and Severity (Any vs. Grade $\geq 3$ )**

The following summary tables of TEAEs will be provided by SOC, PT, and maximum severity (mild < moderate < severe) using frequency counts and percentages:

- Summary tables of TEAEs by SOC, PT, and severity (Any vs. Grade  $\geq 3$ ) will be provided as well.

### 6.3.2. Solicited Adverse Reactions

An AR is any AE for which there is a reasonable possibility that the test product caused the AE. The term “Solicited Adverse Reactions” refers to selected signs and symptoms occurring after injection administration during a specified post-injection follow-up period (day of injection and 6 subsequent days). The solicited ARs are recorded by the subject in eDiary. The occurrence and intensity of selected signs and symptoms is actively solicited from the participant during a specified post-injection follow-up period (day of injection and 6 subsequent days), using a pre-defined checklist (i.e., solicited ARs).

The following systemic ARs will be solicited by the eDiary in booster/third dose analysis: headache, fatigue, myalgia (muscle aches all over the body), arthralgia (aching in several joints), nausea/vomiting, fever, chills, irritability/crying, sleepiness, and loss of appetite.

The AR categories are different for younger population between Age 37 months to <12 years and Age 6 months to  $\leq$  36 months. Details presented in Table 8 and 9 in the protocol.

The solicited ARs will be graded based on the grading scales presented in Table 8 and 9 in the protocol, modified from the Toxicity Grading Scale for Healthy Adult and Adolescent Volunteers Enrolled in Preventative Vaccine Clinical Trials (DHHS 2007). Investigator will assess Grade 4 events (with exception of fever).

If a solicited local or systemic AR continues beyond 7 days post injection, the participant's parent(s)/ LAR(s) will be prompted to capture details of the solicited local or systemic AR in the eDiary until it resolves or the next IP injection occurs, whichever occurs first.

All solicited ARs (local and systemic) will be considered causally related to injection.

After booster doses with mRNA-1273.214, local or systemic ARs will only be reported if they are medically attended, considered serious or lead to discontinuation from the study. No eDiaries will be used after booster doses with mRNA-1273.214.

Analyses of solicited ARs will be provided by age and treatment group for each injection (mRNA-1273 booster or third dose) based on the associated subset of Solicited Safety Set, i.e. Booster/Third Injection Solicited Safety Set, unless otherwise specified.

The number and percentage of subjects who reported each individual solicited local AR (has a severity grade of Grade 1 or greater) and solicited systemic AR (has a toxicity grade of Grade 1 or greater) during the 7-day follow-up period after booster/third dose will be tabulated by age group, vaccination group, toxicity grade, and injection. The number and

percentage of subjects who reported each individual solicited AR will also be summarized by age group, vaccination group, toxicity grade, days of reporting and injection.

The number and percentage of subjects experiencing fever (a temperature greater than or equal to 38.0°C/100.4°F by the oral, axillary, or tympanic route) by toxicity grade will be provided.

A two-sided 95% exact confidence interval (CI) using the Clopper-Pearson method will be provided for the percentage of subjects who reported any solicited local AR, solicited systemic AR, or any solicited AR.

The onset of individual solicited AR is defined as the time point after each injection at which the respective solicited AR first occurred. The number and percentage of subjects with onset of individual solicited AR will be summarized by age group, vaccination group, study day relative to the corresponding injection (Day 1 through Day 7), and injection.

The duration will be calculated as the end date/day of the solicited AR event – start date/day of the solicited AR event + 1, regardless of whether it is intermittent or continued. If the solicited AR continues beyond 7 days, the days a solicited AR is reported after 7 days will be included (e.g., an event that lasted 5 days in the first 7 days post injection and 3 days beyond 7 days post injection, the duration will be reported as 8 (5+3) days.)

### **6.3.3. Pregnancy Tests**

A point-of-care urine pregnancy test will be performed at the Screening Visit (Day 0) and before each vaccine dose. At any time, a pregnancy test either via blood or point-of-care urine can be performed, at the discretion of the investigator.

A by-subject listing will be provided for pregnancy tests for Part 2 open-label phase and booster/third dose analysis separately.

## **6.4. Immunogenicity Analysis**

The analyses of immunogenicity in long-term analysis at Day 1, Day 57, Day 209 and Day 394 (as applicable) will be based on the PP Immunogenicity Subset (Long-term Analysis) and Immunogenicity Subset (Long-term Analysis).

The analyses of immunogenicity in mRNA-1273 booster/third dose analysis will be based on

- PP Immunogenicity Subset with Pre-booster SARS-CoV-2 Negative for booster dose Analysis.

- PP Immunogenicity Subset (including Pre-booster/third dose SARS-CoV-2 Negative and Positive) for booster/third dose Analysis.

The PP Immunogenicity Subset with pre-booster SARS-CoV-2 negative will be used in the primary and secondary immunogenicity analyses for Part 1 and Part 2 booster dose analysis (Not applicable for Part 3 third dose analysis). And PP Immunogenicity Subset will be used for Part 3 third dose analysis, unless otherwise specified. The PP Immunogenicity Subset will be used in the immunogenicity analyses by pre-booster/third dose SARS-CoV-2 status (negative vs. positive).

The GMT and geometric mean (GM) level will be calculated using the following formula:

$$10^{\left\{ \frac{\sum_{i=1}^n \log_{10}(t_i)}{n} \right\}}$$

where  $t_1, t_2, \dots, t_n$  are  $n$  observed immunogenicity values or levels.

The geometric mean fold-rise (GMFR) measures the changes in immunogenicity values or levels within subjects. The GMFR will be calculated using the following formula:

$$10^{\left\{ \frac{\sum_{i=1}^n \log_{10}\left(\frac{v_{ij}}{v_{ik}}\right)}{n} \right\}} = 10^{\left\{ \frac{\sum_{i=1}^n \log_{10}(v_{ij}) - \log_{10}(v_{ik})}{n} \right\}}$$

where, for  $n$  subjects,  $v_{ij}$  and  $v_{ik}$  are observed immunogenicity values for subject  $i$  at time points  $j$  and  $k$ ,  $j \neq k$

